8.1 Deterioration

The number and proportion of participants with deterioration, as defined below, will be tabulated for each treatment group at 3 months as a safety outcome. Treatment group differences will not be reported.

324 325

327

328

329

330

- Deterioration is defined as meeting one of the following criteria at the 3-month follow-up visit:
- 326 1) Constant exotropia at least 10Δ at distance AND near by SPCT:
 - a) Constant is defined as an exotropia present throughout the examination and confirmed by cover/uncover testing performed at least 3 different times over the course of the exam (including during assessment of IXT control).
 - 2) Decrease in near stereoacuity of at least 2 levels from baseline, or to nil, measured using the Randot Preschool Stereotest.

331332333

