Précis	Understanding the effectiveness of intensive patching has important implications for managing children with IXT. If full-time patching is associated with improvement in distance control vs an observation group, then future studies can be conducted to evaluate different durations of full-time patching treatment, whether the effect is maintained off-treatment, and how full-time patching compares to other treatment strategies.
Objectives	Determine whether full-time patching is more effective than observation for improving distance control of IXT after 3 months of treatment (on-treatment outcome).
Study Design	Randomized clinical trial.
Number of Sites	The study is open to all clinical sites approved to participate in the PEDIG network.
Endpoint	
Primary Efficacy Outcome: Change in control of IXT at distance after 3 months based upon the average of three measures of control at distance.
 
Key Safety Outcomes:
 
 1. Deterioration is defined as meeting one of the following criteria at the 3 months follow-up visit: 
 • Constant exotropia $\geq 10\Delta$ at distance AND near by SPCT. Constant is defined as an exotropia present throughout the examination and determined by at least three cover/uncover tests performed at various times during the exam. • Decrease in near stereoacuity on the Randot Preschool Stereotest of at least 2 levels from baseline, or to nil. 2. Decrease in distance visual acuity 3 or more logMAR lines from baseline in either eye or IOD 3 or more logMAR lines. 3. Diplopia ‘More than 2 times per day’ by parental report 4. Diplopia ‘All the Time’ by child symptom survey

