986 The distribution of actual patch wear time will be tabulated overall and by treatment groups. The
987 potential correlation between actual patch wear time in the FT patching group and the change
988 from baseline in the following outcomes will be evaluated at 3 months (when collected):

- 989 1. Distance control score
- 990 2. Near control score
- 991 3. Distance angle of deviation
- 992 4. Near angle of deviation
- 993 5. Level of suppression
- 994 6. Convergence fusional amplitudes
- 995 7. Divergence fusional amplitudes
- 996 8. Symptom survey score
- 997 9. Diplopia assessment by Parent
- 998 10. PedEyeQ score (each domain)

999 A Spearman correlation coefficient and 95% confidence interval will be calculated for each
1000 outcome.

1001 **7.8.2 Outcome of Retinal Correspondence Testing**

1002 The relationship of retinal correspondence response with respect to the following outcomes
1003 within each treatment group will be evaluated at 3 months:

- 1004 1. Distance control score
- 1005 2. Near control score
- 1006 3. Distance angle of deviation
- 1007 4. Near angle of deviation
- 1008 5. Level of suppression
- 1009 6. Convergence fusional amplitudes
- 1010 7. Divergence fusional amplitudes
- 1011 8. Symptom survey score
- 1012 9. Diplopia assessment by Parent
- 1013 10. PedEyeQ score

1014 For continuous outcome variables, the difference in means between participants with normal
1015 versus anomalous retinal correspondence will be calculated along with a 95% confidence
1016 interval. For categorical outcome variables, the difference in proportions between participants
1017 with normal versus anomalous retinal correspondence will be calculated along with a 95%
1018 confidence interval.

1019 **7.8.3 Subgroup Analysis of Distance Control**

1020 The treatment group comparison of distance control will be assessed at 3 months in subgroups
 1021 based on gender and race/ethnicity in accordance with NIH guidelines; however, no effect
 1022 modification is expected for these factors.
 1023

1024 **7.9 Safety Analyses**

1025

1026 **7.9.1 Deterioration**

1027 The number and proportion of participants with deterioration, as defined below, will be tabulated
 1028 for each treatment group at 3 months as a safety outcome.

1029 Deterioration is defined as meeting one of the following criteria at the 3 months follow-up visit:
 1030

- 1031 1. Constant exotropia at least 10Δ at distance **AND** near by SPCT:

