Categorical outcomes will be described by tabulating the number and percentage falling into each category by treatment group at baseline and 3 months. For binary / dichotomized outcomes, the treatment group difference in percentages with the outcome at 3 months and 95% confidence interval will be estimated by inverting Barnard's test, using the method of Agresti and Min.² For multichotomous outcomes, no treatment group differences, or CIs, will be estimated as the sample sizes in each treatment group are small and sample size per outcome category is likely to be sparse.

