4.5 Binocular Diplopia by Parental Report

The number and proportion of participants with binocular diplopia at 3 months with a frequency of "more than 2 times per day" over the last week at distance and near separately (by parental report) will be tabulated by treatment group and analyzed as a dichotomized outcome.

226 227

228

229

230

5 Patch Wear Time

Site staff will activate and distribute occlusion dose monitors (ODMs) for participants randomized to patching (patching adherence is not applicable to the observation group). While activated, the ODM takes a temperature reading every 20 minutes, which is used to determine whether the patch was being worn at that time.

231232

233234

235

The sensors hold 133 days of data when the time interval is set at 20 minutes. If the sensor has not been read and data downloaded for a longer period than the max storage allows (133 days), the oldest data is overwritten, so only the latest 133 days will be uploaded.

236237238

239

For days with sensor readings, the temperature threshold for considering the patch worn will be \geq 82°F (\geq 27.78 °C), versus < 82°F (27.78 °C) for not worn.⁵

For each participant in the full-time patching group, the following statistics will be reported:

240241242

• Number of participants (% of total in patching group) with ODM data.

243244245

 Distribution (median, IQR, minimum, maximum, histogram) of the percentage of days for which ODM data was obtained, including all participants randomized to full-time patching.

246247248

Percentage of days for which ODM data was obtained = (number of days for which ODM data was obtained (regardless of completeness))/(expected number of days of patching) * 100%.

249250251

Expected number of days of patching = (Date of randomization – date of 3-month visit) – 2, since expected to patch day after randomization and stop patching the day before their 3-month visit.

252253

 Number of participants (% of total in patching group) with no ODM data.

254255

Of those with data, the distribution of the number of days patching will be split into quartiles

256257

• Within each quartile, the number of participants (% of total in patching group) will be calculated.

258259

• Distribution (median, IQR, minimum, maximum, histogram) of total number of hours patched in patching group participants with ODM data

260 261 O Total number of hours patched = (Number of readings exceeding 82 degrees Fahrenheit) x 20 minutes x (1 hour / 60 minutes)

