8.2 Reduction of Distance Visual Acuity

Any cases of 1) interocular difference $\ge 0.3 \log MAR$ and 2) reduced visual acuity in best refractive correction ($\ge 0.3 \log MAR$) in either eye will be tabulated by treatment group at 3 months.

336337

341

343

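### SAP 8.1 bars a between-arm difference for deterioration without giving a reason, although the SAP's own exact interval would show how little sparse counts can exclude

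*SAP*

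**What the plan says.** - Protocol synopsis, Endpoint: four key safety outcomes, of which the first begins "Deterioration is defined as meeting one of the following criteria at the 3 months follow-up visit". A child meets it either through constant exotropia at both distances or through a loss of near stereoacuity, so it is a yes/no outcome.
- Protocol 7.9.1: "The number and proportion of participants with deterioration, as defined below, will be tabulated" for each arm. It neither plans nor forbids a between-arm difference.
- SAP 8.1: the same tabulation and definition, plus "Treatment group differences will not be reported". No reason is given.
- SAP 8.2: two visual acuity conditions, an interocular difference of at least 0.3 logMAR and a loss of at least 0.3 logMAR, the latter "in either eye will be tabulated by treatment group at 3 months". There is no bar on a difference here.
- SAP 8.3: diplopia, by child and by parent, is tabulated by arm.
- SAP Section 4, binary exploratory outcomes: the "difference in percentages with the outcome at 3 months and 95% confidence interval will be estimated by inverting Barnard's test" (Agresti and Min), with no p-values. The exception reads "For multichotomous outcomes, no treatment group differences, or CIs, will be estimated as the sample sizes in each treatment group are small".
- SAP 4.5: parent-reported diplopia more than twice a day, which is also a key safety outcome, is "tabulated by treatment group and analyzed as a dichotomized outcome" and so receives that interval.

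**The concern.** A randomised trial gives an unconfounded comparison of harm between arms. For its first-listed safety outcome, this plan rules out stating that comparison. The likely result is a table with very few events, and such a table is easy to misread. No events in either arm can pass for evidence that patching does not cause deterioration, and a small imbalance can pass for evidence that it does. An interval for the difference shows what size of excess the data can and cannot exclude. The SAP already specifies a suitable small-sample method and applies it to other binary outcomes. The only small-sample reason it gives for omitting differences is confined to multi-category outcomes.

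**Working it through.** **Inputs.** From Protocol 7.3: 34 completers per arm (68 in total), 36 per arm enrolled, SD of change 1.5, baseline-change correlation 0.30, difference 1.15 points, two-sided 5% test, 90% power, 5% loss. SAP Section 8 uses observed, in-window data only, so 34 is the expected denominator. The documents give no 3-month deterioration rate, so the event counts below are assumptions.

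**Step 1: reproduce the plan's sample size.** The covariate-adjusted SD is 1.5 × √(1 − 0.30²) = 1.431. By the normal approximation, n per arm = 2 × (1.960 + 1.282)² × 1.431² / 1.15² ≈ 32.5, so 33 per arm and 66 in total. The noncentral-t version with N − 3 degrees of freedom gives 34 per arm, 68 in total, with 90.4% power. It also matches all nine cells of Protocol Table 2. Then 68 / 0.95 = 71.6, which rounds up to 72. The plan's figures reproduce. The documents state no precision or power for deterioration.

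**Step 2: what counts are plausible.** Protocol 1.2.1 gives two figures for observed children aged 3 to under 10 in the earlier part-time patching trial.
- At the 3-year visit, 1 of 132 untreated children met motor or stereoacuity criteria: 34 × 1/132 ≈ 0.3 expected events per arm.
- By 3 years, 25 of 183 had deteriorated, of whom 12 were treated without meeting those criteria. That leaves 13 of 183 (7.1%): 34 × 13/183 ≈ 2.4 expected events.

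Neither is a 3-month rate, the earlier definition differs slightly, and neither describes full-time patching. They do make counts between 0 and a handful per arm realistic.

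**Step 3: exact interval for the difference.** For each candidate difference d, the score statistic is T(d) = (p₁ − p₂ − d) / √[p̃₁(1 − p̃₁)/n + p̃₂(1 − p̃₂)/n], where p̃₁ and p̃₂ are the maximum likelihood estimates under p₁ − p₂ = d. The two-sided p-value is the largest probability, over the nuisance proportion, of a table with |T| at least as large as that observed. The 95% interval keeps every d with p > 0.05, searched in steps of 0.2 points. This is the kind of inversion that the SAP cites.

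Results are patching minus observation, in percentage points, with 34 per arm:

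| Assumed events | Difference | Exact 95% interval |
|---|---|---|
| 0 v 0 | 0.0 | -11.0 to +11.0 |
| 1 v 0 | +2.9 | -8.2 to +16.0 |
| 2 v 0 | +5.9 | -5.0 to +20.4 |
| 3 v 0 | +8.8 | -2.0 to +23.4 |
| 4 v 1 | +8.8 | -5.0 to +24.2 |
| 5 v 0 | +14.7 | +3.6 to +30.8 |

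With all 36 enrolled per arm observed, 0 v 0 gives -10.4 to +10.4, so the choice of denominator hardly matters.

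**Step 4: one arm alone.** The upper limit of the two-sided exact 95% interval for 0 of 34 is 1 − 0.025^(1/34) = 10.3%.

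**The case against.** The strongest reply is that SAP Section 8 is descriptive throughout and follows the protocol. Protocol 7.9.1 plans only a tabulation, Protocol 5.2 does the same for acuity and stereoacuity loss, and the trial is powered for efficacy alone. Counts and proportions are reported for each arm, so a reader can derive an interval, and descriptive safety tables are ordinary in a trial of this size. All of this stands, and it keeps the point small. It does not explain why a difference should be forbidden rather than left unplanned, and an exact unconditional interval is not a hand calculation.

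A reader might infer more than the documents support, in four ways.
- *That the SAP treats its safety outcomes inconsistently within Section 8.* It does not: SAP 8.3 also only tabulates parent-reported diplopia. The interval in SAP 4.5 arises because Protocol 7.7.8 had separately made that variable a secondary endpoint, which deterioration never was.
- *That the SAP drops an analysis the protocol promised.* No protocol text plans a between-arm safety estimate.
- *That Protocol 1.9.1 relies on the arm comparison to detect harm.* That section describes assessing the criteria at 3 months so that the individual child's treatment can be reconsidered.
- *That SAP 8.2 carries the same bar.* It is silent on differences.

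Nor does any passage plan a claim that patching is free of this harm. The risk of misreading is a judgement about how a sparse table will be received.

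**Conclusion.** The point holds as a reporting weakness. SAP 8.1 contains an unexplained bar that goes beyond the protocol, and it withholds from the first-listed key safety outcome an estimate that the SAP already gives for other binary outcomes. At 34 completers per arm, even an empty table leaves differences of about 11 points in either direction open, and 3 v 0 still allows an excess of up to about 23 points. The intervals rest on the planned number of completers and on assumed counts; different counts would move them, but they would stay wide at this sample size. There is no calculation error and no effect on the primary analysis or its conclusion. It ranks as desirable rather than necessary.

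**What to change.** Replace the last sentence of the opening paragraph of SAP 8.1 with: *The treatment group difference in the proportion with deterioration and its 95% confidence interval (Agresti and Min) will be reported without a p-value.*

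Optionally, add the same sentence to SAP 8.2, once for an interocular difference of at least 0.3 logMAR and once for a loss of at least 0.3 logMAR in either eye, with a separate interval for each condition and no composite.

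The cost is one sentence (three with the option). The code is already needed for SAP 3.1, 3.2, 4 and 6, no new data are collected, and no test is added, so there is no multiplicity cost. The drawback is that the intervals will be wide, and the report should say so plainly.

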8.2 Reduction of Distance Visual Acuity

Any cases of 1) interocular difference $\ge 0.3 \log MAR$ and 2) reduced visual acuity in best refractive correction ($\ge 0.3 \log MAR$) in either eye will be tabulated by treatment group at 3 months.

336337

341

343

8.3 Diplopia

- At 3 months, frequency of diplopia by child survey will be tabulated for each treatment group as "Never",
- 'Sometimes', or "All the Time". By parent survey, the responses will be tabulated by treatment group as
- "No", "2 times or less per day", and "More than 2 times per day".

9 Additional Tabulations

- The following additional tabulations will be performed:
 - A flow chart accounting for all participants according to treatment group
- Number and percentage completing the visit by treatment group
- Baseline demographics and clinical characteristics overall and by treatment group at randomization
- Protocol deviations by treatment group

References

348

361

- 349 1. Benjamini Y, Krieger AM, Yekutieli D. Adaptive linear step-up procedures that control the false
- discovery rate. *Biometrika*. 2006;93(3):491-507. doi:10.1093/biomet/93.3.491
- 351 2. Agresti A, Min Y. On small-sample confidence intervals for parameters in discrete distributions.
- 352 *Biometrics*. Sep 2001;57(3):963-71. doi:10.1111/j.0006-341x.2001.00963.x
- 353 3. Hatt SR, Leske DA, Liebermann L, Mohney BG, Holmes JM. Variability of angle of deviation
- measurements in children with intermittent exotropia. JAAPOS. Apr 2012;16(2):120-4. doi:S1091-
- 355 8531(12)00074-2 [pii]
- 356 10.1016/j.jaapos.2011.11.008
- 357 4. SF O, J A. Parametric ANCOVA and the Rank Transform ANCOVA When the Data are
- 358 Conditionally Non-normal and Heteroscedastic. *J Educ Stat.* 1984;9(2):129-149.
- 359 5. Wang J, Jin J, Malik A, et al. Feasibility of monitoring compliance with intermittent occlusion
- therapy glasses for amblyopia treatment. *J AAPOS*. 2019;In Pressdoi:10.1016/j.jaapos.2019.04.009

Page 11 of 11

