 - Deliberate overminus is defined for this protocol as any refractive correction prescribed to yield lenses that are overminused by more than -0.50D SE than cycloplegic refraction SE.
 - Less than the full cycloplegic hyperopic correction (i.e., prescribing reduced plus) or no correction for a hyperopic SE refractive error is not considered the same as overminusing for this protocol (because most patients without IXT but with hyperopic SE refractions up to +2.00 D SE would not typically be prescribed a refractive correction.)
 - Note that the refractive correction guidelines and the requirement to wear refractive correction for at least 2 weeks apply not only to participants who require refractive correction under the above criteria but also to any other participant who is wearing refractive correction.
 8. Gestational age > 30 weeks

- 382 9. Birth weight > 1500 grams
383 10. Patient and/or parent understands protocol, is willing to enroll, and is willing to accept
384 that other treatment for IXT will not be offered for 3 months
385 11. Parent has phone and is willing to be contacted by Jaeb Center staff
386 12. Relocation outside of area of an active PEDIG site within next 3 months not anticipated
387

388 **2.2.2 Exclusion Criteria**

389 Individuals meeting any of the following criteria at baseline will be excluded from study
390 participation.

- 391 1. Prior strabismus, intraocular, or refractive surgery (including BOTOX injection)
392 2. Prior nonsurgical treatment for IXT (e.g., patching, vergence therapy, vision
393 therapy/orthoptics, base-in prism, or deliberate overminus with spectacles more than
394 1.00 D) for >1 week duration within the past 1 year
395 3. Previous amblyopia treatment other than refractive correction
396 4. Diplopia more than 2 times per day by parental assessment
397 5. Paretic or restrictive strabismus
398 6. Craniofacial malformations affecting the orbits
399 7. Ocular disorders which would reduce VA (except refractive error)
400 8. Severe developmental delay that would interfere with treatment or evaluation (in the
401 opinion of the investigator). Participants with mild speech delay or reading and/or
402 learning disabilities or ADHD are not excluded.
403 9. Neurological anomaly that could affect ocular motility (e.g., cerebral palsy, Down
404 syndrome)
405 10. Immediate family member (child or sibling) of any investigative site personnel directly
406 affiliated with this study.

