407 11. Known allergy to adhesive patches.
408 12. Known allergy to silicone.
409

410 **2.3 Historical Information**

411 Historical information elicited will include the following: date of birth, sex, race, ethnicity,
412 spectacle correction, and prior treatment for IXT and amblyopia.
413

414 **2.4 Screening and Baseline Procedures**

415 Testing will be done in the order specified below on a single day following enrollment in the
416 child's current refractive correction if worn (any spectacle correction worn must meet the criteria
417 specified in section 2.2) and without cycloplegia:

- 418 1. Eye-Related Quality of life: Pediatric Eye Questionnaire (PedEyeQ)
419 • Child questionnaire: Completed by children 5 years and older
420 • Parent questionnaire: Completed by the parent for all children regardless of age
421 (includes parent and proxy questions)
422 2. Symptom Survey:
423 • Intermittent Exotropia Symptom Survey completed by children 5 years or older.
424 • Single diplopia question to be completed by children 3 or 4 years.

- 425 3. Diplopia Assessment by Parent: Assess diplopia presence and frequency over the last week,
426 by parental report. If present, classify diplopia frequency as “2 times or less per day” or
427 “more than 2 times per day.”
- 428 4. Monocular Distance VA Testing: Distance VA testing will be performed by a certified
429 examiner on a certified VA system (EVA or M&S), using the ATS single surround HOTV
430 for participants 3 to <7 years old and using the E-ETDRS for participants ≥ 7 years. The
431 same VA testing method used at enrollment will be used again at 3 months.
- 432 5. Stereoacuity Testing: Assessed using the Randot Preschool Stereotest at near (performed at
433 40 cm) as outlined the *IXT7 Procedures Manual*
- 434 6. Control of the Exodeviation #1: Control of the exodeviation at distance (6 meters) then near
435 (1/3 meter) will be assessed using the standardized IXT control scale,³⁵ as outlined in the
436 *IXT7 Procedures Manual*.
- 437 • Testing must be performed by a pediatric ophthalmologist, pediatric optometrist, or
438 certified orthoptist.
 - 439 • The same examiner must assess control for all three assessments of control at each
440 visit.
- 441 8. Divergence Amplitude Testing: Measured at distance (6 meters) using the PEDIG-approved
442 prism bar as described in the *IXT7 Procedures Manual*
- 443 • Testing must be performed by a pediatric ophthalmologist, pediatric optometrist, or

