 - 1032 ○ Constant is defined as an exotropia present throughout the examination and
 - 1033 confirmed by cover/uncover testing performed at least 3 different times over the
 - 1034 course of the exam (including during assessment of IXT control).
- 1035 2. Decrease in near stereoacuity of at least 2 levels from baseline, or to nil, measured using
 1036 the Randot Preschool Stereotest.

1037 **7.9.2 Reduction of Distance Visual Acuity**

1038 Any cases of 1) interocular difference ≥ 0.3 logMAR and 2) reduced visual acuity in best
 1039 refractive correction (≥ 0.3 logMAR) in either eye will be tabulated by treatment group at 3
 1040 months.

1041 **7.9.3 Diplopia**

1042 After 3 months, any new cases of diplopia ‘Sometimes’ or ‘All the Time’, based on response to
 1043 item 8 from the IXT symptom survey (asked as a single question for children ages 3 and 4 years
 1044 of age) will be tabulated for each treatment group. In addition, diplopia occurring ‘Never’,
 1045 ‘Sometimes’, or ‘All the Time’ will also be tabulated for each treatment group.
 1046

1047 **7.10 Patching Adherence**

1048 Patching adherence (as reported by the parent) will be tabulated at the 3-month visit for the FT
 1049 patching treatment group, as will reasons for any major deviations.

1050 **7.11 Additional Tabulations and Analyses**

1051 The following tabulations and analyses will be performed:

- 1052 ● A flow chart accounting for all participants according to treatment group
- 1053 ● Visit completion rates according to treatment group
- 1054 ● Baseline demographics and clinical characteristics overall and by treatment group at
 1055 randomization
- 1056 ● Protocol deviations according to treatment group

1057

Chapter 8: Data Collection and Monitoring

1058 **8.1 Case Report Forms and Other Data Collection**

1059 The main study data are collected on electronic case report forms (CRFs). When data are directly
1060 collected in electronic case report forms, this will be considered the source data. For any data
1061 points for which the eCRF is not considered source (e.g., lab results that are transcribed from a
1062 printed report into the eCRF), the original source documentation must be maintained in the
1063 participant's study chart or medical record. This source must be readily verifiable against the
1064 values entered into eCRF. Even where all study data are directly entered into the eCRFs at office

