adherence to match data published after SAP draf (Section 5). Required subgroup analy have at least 10 observat per treatment arm for ana (Section 7). Updated diplopia tabulat to match case report form (Section 8).	must or sitivity cipants ace of 2 stage on 3). sensor fted syses to tions alysis tions m	Clarified criteria for sensitival analysis excluding participate with interocular difference of lines (Section 2). Clarified that the false discovery rate will be controlled for secondary outcomes using the two-stag step-up procedure (Section 3). Edited threshold for exploratory temperature sense adherence to match data published after SAP drafted (Section 5). Required subgroup analyses have at least 10 observations per treatment arm for analys (Section 7). Updated diplopia tabulations to match case report form	06May2025	[name]			1.2

Signature Page

Signature of Author: [name] [name]

I agree to the terms defined by the placement of my

document signature in this document

2025-05-06 11:29-04:00 Signature in this docume 2025-06-02 08:21-04:00

Signature of Approver:

[name]

I agree to the terms defined by the placement of my signature in this

document

2025-05-06 11:22-04:00

1 Purpose of IXT7 Study

The objective of the IXT5 study is to determine whether 3 months of full-time patching is more effective than observation for improving distance control of IXT (on-treatment outcome). A total of 72 participants will be randomly (1:1) assigned to the following treatment groups:

• Observation for 3 months – no treatment other than refractive correction

Full-time (FT) patching (all waking hours) for 3 months (right eye on even days, left eye on odd days), in addition to refractive correction

2 Primary Analysis – Efficacy of Full-Time Patching (3 Months, On-Treatment)

The primary outcome is change from baseline to 3 months in mean (of 3 measurements) distance control score (mean 3-month score – mean baseline score). Single control scores are integer-valued and range from 0 to 5 with 0 indicating no deviation (no tropia or phoria) and 5 indicating constant tropia. To meet eligibility criteria, the mean score must be ≥ 2.0 and ≤ 5.0 points. Hence, the change in mean control score is a quasi-continuous, bounded measurement with possible values ranging from -5.0 to 3.0 points, with negative values indicating improvement and positive values indicating worsening.

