4.3 IXT Symptom Survey Score

A 7-item IXT Symptom Survey will be completed by children aged 5 years and older at the enrollment and 3-month exams. For each IXT-specific symptom, the child is asked how often it occurs, using the response choices of "never" "sometimes", and "all the time." The distribution for each individual item will be tabulated for each treatment group at both baseline and 3 months. The symptom survey will not be Raschscored, and no estimates of between treatment group differences will be obtained.

Children who were less than 5 years old at the time of enrollment will not complete the survey. Instead, they will be asked a single question: "Do you have double vision (see two of things when you know there is really only one)?", with the ability to respond with "never" "sometimes", or "all the time." The distribution

of responses will be tabulated for each treatment group at both baseline and 3 months. No estimates of between treatment group differences will be obtained.

214215216

217

218

219

220

213

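### SAP 8.3 leaves out the count of new child-reported diplopia cases that protocol 7.9.3 specifies

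*SAP*

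**What the plan says.** Protocol 7.9.3 uses the child's own answer to item 8 of the symptom survey, which is asked as a stand-alone question at ages 3 and 4. It plans two tabulations. The first is of onset: "After 3 months, any new cases of diplopia" at *Sometimes* or *All the Time*, by arm. The second is the distribution over all three response levels. The text marks it as a further table: "of age) will be tabulated for each treatment group. In addition, diplopia occurring" at each level is tabulated too.

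SAP 8.3 has one child-survey table: "At 3 months, frequency of diplopia by child survey will be tabulated for each treatment group as" *Never*, *Sometimes* or *All the Time*. It adds a parent table that protocol 7.9.3 does not have: "By parent survey, the responses will be tabulated by treatment group as" none, 2 times or less per day, or more than 2 times per day. Neither sentence mentions new cases or baseline status. The SAP revision log gives this reason for the edit to Section 8: "Updated diplopia tabulations to match case report form".

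On entry, protocol 2.2.2 excludes "Diplopia more than 2 times per day by parental assessment". No criterion refers to the child's own report. On data, protocol 2.4 and 3.4 collect the same items at both visits: the survey from age 5, the parent assessment at all ages, and for the youngest, "Single diplopia question to be completed by children 3 or 4 years".

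**The concern.** Protocol 1.9.1 names troublesome diplopia first among the risks of patching, and describes it as something patching may create. That is a question about onset. A 3-month distribution shows how many children report diplopia, not how many began to report it after randomization.

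Most other safety outcomes in SAP section 8 either refer to baseline (loss of stereoacuity, reduced acuity) or use a level that entry rules out (an interocular difference of 0.3 logMAR or more, against an entry limit of 2 lines). Child-reported diplopia has neither safeguard. If the SAP is followed as written, a tabulation that the protocol specifies is not produced.

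**Working it through.** The plan states no figure for this point, so there is none to reproduce. The check compares the texts and then asks what the remaining tables can recover.

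**Which responses can be present at entry.** Only parent-reported diplopia more than 2 times per day is excluded. Three cases follow:
- Child report of *Sometimes* or *All the Time*: possible at baseline, so a 3-month case may be old or new.
- Parent report of 2 times or less per day: possible at baseline, with the same ambiguity.
- Parent report of more than 2 times per day: not possible at baseline in an eligible child, so any 3-month case is new or worsened.

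**Whether other SAP tables fill the gap.** SAP 4.3 tabulates child responses "for each treatment group at both baseline and 3 months", and the general rule for categorical outcomes in SAP section 4 does likewise. These are two separate distributions, not a record of change within each child. SAP 4.3 also describes a 7-item survey, whereas protocol 4.1 describes 22 items with diplopia as item 8. It is therefore not certain that the diplopia item for children aged 5 or older is in that table.

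**What separate tables can recover.** Let N children in an arm have both visits, a be positive at baseline and b positive at 3 months. If p are positive at both, new cases = b − p. Since p lies between max(0, a + b − N) and min(a, b), new cases lie between max(0, b − a) and min(b, N − a). Here *new* means *Never* at baseline and either positive level at 3 months, which is the natural reading of 7.9.3.

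Protocol 7.3 plans for 34 completers per arm, so N = 34. The values of a and b are assumed, because the documents give none.

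| a (baseline) | b (3 months) | Lower: max(0, b − a) | Upper: min(b, 34 − a) |
|---|---|---|---|
| 0 | 2 | 2 | 2 |
| 0 | 6 | 6 | 6 |
| 2 | 2 | 0 | 2 |
| 4 | 4 | 0 | 4 |
| 6 | 6 | 0 | 6 |
| 4 | 6 | 2 | 6 |

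With no baseline cases, the 3-month count is the new-case count. With any baseline cases, the two tables give a range. The 3-month table alone gives only the upper limit b. The bounds also assume that the same children contribute to both tables.

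**The case against.** Several points on the other side have force.

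- **Diplopia may be rare at entry.** Protocol 1.1 says it is rarely reported in this condition, and 1.9.1 says diplopia from patching is seldom reported. A reader might infer from the entry criteria that pre-existing cases are common. The criteria show only that such cases are allowed. This stands, and it limits the likely size of the problem.
- **The SAP did not swap one table for a weaker one.** A reader might infer a substitution. The protocol already planned the frequency table; the SAP keeps it and adds a parent table. What happened is an omission.
- **The synopsis outcomes are still reported.** The synopsis lists parent-reported diplopia more than 2 times per day and child-reported *All the Time*, neither restricted to new cases. SAP 8.3 shows both levels, and SAP 4.5 gives a between-arm difference and 95% confidence interval for the parent one. The need to count new cases comes from 7.9.3 alone.
- **Randomization still informs causation.** A reader might infer that the trial could no longer tell whether patching causes diplopia. The arms can be compared at 3 months, pre-existing diplopia is balanced in expectation, and equal numbers of new and resolved cases in one arm would not show causation by themselves. This also stands, although with about 34 children per arm chance imbalance is possible.

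None of this explains the omission. Matching the case report form accounts for the response categories, but not for dropping a count that can be derived from items collected at both visits.

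**Conclusion.** The point holds in a narrow form. SAP 8.3 omits the per-arm count of new child-reported diplopia that protocol 7.9.3 specifies, and no other planned table recovers it unless no child is positive at baseline. The ambiguity covers the child responses and the lower parent category. It does not reach parent-reported diplopia more than 2 times per day.

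The size is unknown, because the documents give no baseline rate. With equal assumed counts of 2, 4 or 6 of 34 at both visits, the number of new cases could be anything from 0 up to that count. With a rate near zero, the loss is negligible. A reader might also infer that the protocol requires worsened cases or parent-reported onset to be counted. Protocol 7.9.3 mentions neither. The priority is low. The case for acting is that the SAP departs from the protocol on the first-named risk of patching and that the remedy is simple.

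**What to change.** In SAP 8.3, restore the number of new child-reported cases per arm as in protocol 7.9.3. Derive it from a baseline-by-3-month cross-tabulation of the child response, using item 8 of the survey or the single question at ages 3 and 4. State that *new* means *Never* at baseline and *Sometimes* or *All the Time* at 3 months, and give the number of children with both responses as the denominator. Keep the existing 3-month distributions.

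A matching cross-tabulation of the parent response would be a sensible option, but 7.9.3 does not require it. If the count was left out on purpose, the SAP should say so and give the reason.

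The cost is one extra table, with no new data, visits or tests.
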